Patients will be recruited from the emergency department at the participating hospitals. All patients with open fractures (fractures associated with a skin wound) who present to emergency department will be assessed for inclusion. The initial assessment of open fracture will be identified by the emergency room physician who will discuss with the attending on call. The orthopaedic attending will determine if this child is amenable to non-operative treatment and would be considered for study inclusion.

All children will be given antibiotics (Ancef 25mg/kg up to 1gm, or clindamycin if allergic to first generation cephalosporin or penicillin) and if the inclusion criteria are met, will be offered to participate in the study by the orthopaedic surgeon or their delegate. If the patient refused study inclusion, they will then be treated per the attending treating physician recommendation.

If the patient agrees to participate he/she will be randomized. The randomization chart is saved in the REDCap database and functions to randomly assign a patient who is entered into the database into a treatment group, stratifying by site. The attending physician will be responsible for determining the randomization assignment by either (1) logging into the REDCap database to enter the patient and randomize them or (2) calling the research coordinator or his/her representative who will then log in to REDCap to randomize the patient. As a backup, the research coordinator will have the randomizations for each site in numbered, sealed envelopes. The study coordinator will be available 24 hours a day to provide the randomization assignment, the consent form (see consent process below), and answer questions prior to treatment arm assignment. Children in both arms of the study will receive emergency room irrigation with one liter of normal saline, realignment/reduction of the fracture, and casting. Conscious sedation will

usually be necessary for this to occur. Patients will be admitted and have up to 24 hours from the time of injury to make a final decision.

No difference in outcomes have been shown in patients with open fractures treated with operative debridement in less than 6 hours compared with those treated from 6 to 24 hours.(8) The surgical timing will be determined by the attending orthopaedic surgeon.

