Baseline assessment will include the child's age, mechanism of injury, bone fractured, wound side and location, state of skin injury, whether gross contamination is present, neurovascular status, comorbid conditions.

Additionally, if patients do not wish to be randomized to a treatment arm, they will still be presented with an option for study enrollment. They may take part in a prospective chart review in which the same data will be collected as those patients who were randomized. The data collected at both the baseline and follow-up will match the data collected from patients who randomized to a treatment arm. Patients will consult with their physician regarding treatment for their injury and decide which treatment method they prefer. They will then be consented by the study coordinator or an investigator who will describe the study and the data that will be gathered from their medical charts.

Intervention allocation:

The randomization assignment will be completed and accessible only by the study coordinator. The coordinator will have the assignments in numbered, sealed, radio opaque envelopes in sequential order by the study site. The envelopes will be made by an independent study assistant and determined by block allocation with a 1:1 ratio of operative room vs. emergency room management with permuted, mixed blocks of 4 and 6 created randomly. Randomization will be stratified by each center but by no other factors. The order of these permuted blocks will be determined by random number chart.

Experimental and Control Interventions:

Children will be randomized into two treatment arms – formal operative management (OR) and emergency department (ED) management. Children randomized to the OR arm will be taken to the OR within 24 hours for irrigation and debridement and appropriate bone management. Patients who randomize to non-operative treatment will only be given conscious sedation in the emergency department where the bone will be reduced and casted and the wound will be washed out with one liter of normal saline. All patients will be admitted for 24 hours of intravenous antibiotics post treatment and then sent home with 7 days of oral antibiotics.

Follow up visit description and schedule:

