The following are power estimates based on 10000 simulations under the above conditions for various feasible sample sizes. We also obtained power estimates for the scenario involving a 2% infection rate in the control group (OD).

Sample size/arm	Reference Proportion	Power ($\Delta=0.03$)	Power ($\Delta=0.04$)	Power ($\Delta=0.05$)	Power ($\Delta=0.06$)
70	0.01	0.5091	0.6766	0.8536	0.866
80	0.01	0.5164	0.8107	0.8382	0.9434
90	0.01	0.4865	0.786	0.8734	0.9489
100	0.01	0.7416	0.7878	0.9254	0.9616
110	0.01	0.6994	0.8383	0.9245	0.976
120	0.01	0.6926	0.894	0.9437	0.9763
130	0.01	0.714	0.8738	0.9621	0.981
140	0.01	0.6907	0.8783	0.9624	0.99
150	0.01	0.7606	0.9111	0.9748	0.9928
160	0.01	0.8221	0.9394	0.9816	0.997
170	0.01	0.795	0.9427	0.9842	0.998
180	0.01	0.821	0.9339	0.9876	0.9984
190	0.01	0.8147	0.9573	0.9936	0.9987
200	0.01	0.848	0.9629	0.9928	0.9987
210	0.01	0.8503	0.9669	0.9941	0.9995
220	0.01	0.8675	0.9743	0.9961	0.9992
130	0.02	0.4748	0.6378	0.8123	0.9066
140	0.02	0.4906	0.6922	0.8385	0.9288
150	0.02	0.5051	0.7048	0.8785	0.9466
160	0.02	0.5642	0.7452	0.8678	0.9593

170	0.02	0.5458	0.7621	0.8958	0.9679
180	0.02	0.5651	0.7737	0.9165	0.9682
190	0.02	0.5864	0.8088	0.9317	0.9733
200	0.02	0.5865	0.8005	0.9275	0.9807
210	0.02	0.6349	0.8346	0.943	0.9833
220	0.02	0.61	0.842	0.9504	0.9868

For outcome of healing time (**Specific Aim 2**), most fractures have a healing time of 6 weeks with an estimated standard deviation of 1 week. We will again try to show ED management is not inferior with respect to healing time when compared to OR management, assuming a margin of non-inferiority of one week ($\Delta=1$). Assuming a one-sided 0.025 level of significance and power ($1-\beta$) equal to 0.90, the number of subjects required per treatment group can be calculated as follows:

$$H_0: \mu_C - \mu_T \geq \Delta \quad \text{vs.} \quad H_1: \mu_C - \mu_T < \Delta$$

$$N = \frac{2(Z_{\alpha} + Z_{1-\beta})^2 \sigma^2}{\Delta^2}$$

$$N = \frac{2(1.96 + 1.282)^2 1^2}{1^2} \qquad N = 21$$

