We will use an independent two-sample confidence interval for binomial proportions comparing infection rates between the two treatment arms. If the upper limit of a two-sided, 95% confidence interval is less than the margin of non-inferiority, we will have evidence that ED management is not inferior to OR management. Similarly, an independent two-sample confidence for difference in mean healing time will be constructed and used in the same manner to determine evidence of non-inferiority. Both large sample, normal approximation methods and exact methods will be explored. Descriptive data will be used to relay anesthesia complications, additional procedures and significant infections. Primary analysis will be based on the "as treated" principle, and an intent-to-treat analysis will also be conducted. We expect almost no cross-over in the initial 24 hours after injury. We will also use Kaplan-Meier estimation to create curves comparing cumulative incidence of infection as well as time to healing for the duration of study follow-up.

Data Security:

Research Electronic Data Capture (REDCap)

REDCap is a secure application used for managing online databases for collecting research data. The software allows data to be stored over a secure web connection with authentication and data logging features. The database creates a log of all activity including information such as the date, time and user who performed the action. The database is password protected and only approved users are able to access projects through REDCap. Data for all sites involved in this multi-center project will be stored in this electronic database. PIs and research coordinators from each site

will be assigned Northwestern University Affiliate NetIDs which will give them access to REDCap through Northwestern University Clinical and Translational Sciences Institute (NUCATS). Once these NetIDs are granted, the research coordinator at Lurie Children's will then add these individuals to the REDCap project.

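### Randomisation is stratified by centre but the healing-time comparison leaves centre out; if centres differ, the interval is somewhat too wide and the as-treated estimate can be biased (minor)

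*Combined protocol and SAP*

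**What the plan says.** Two places in section E (Methods) describe the allocation. Under Study Procedures, the REDCap list is said to "randomly assign a patient who is entered into the database into a treatment group, stratifying by site". Under Intervention allocation, the scheme is "block allocation with a 1:1 ratio of operative room vs. emergency room management with permuted, mixed blocks of 4 and 6 created randomly", and "Randomization will be stratified by each center but by no other factors".

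The Data Analysis section that follows Data management gives the comparisons. For infection: "We will use an independent two-sample confidence interval for binomial proportions comparing infection rates between the two treatment arms". For healing time: "an independent two-sample confidence for difference in mean healing time will be constructed and used in the same manner". As-treated is named as the primary analysis and intent-to-treat as an additional one. Kaplan-Meier curves are planned for both outcomes, and the Final analysis paragraph adds only confidence intervals and the same curves.

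The sample size section assumes for healing that "most fractures have a healing time of 6 weeks with an estimated standard deviation of 1 week", "assuming a margin of non-inferiority of one week". Centre does not appear in any sample size calculation or analysis.

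**The concern.** Permuted blocks within each centre keep the arms nearly balanced at every site. Differences in healing time between sites then largely cancel out of the arm comparison. An unstratified standard error still counts those differences as noise, so the interval overstates the uncertainty of the randomised comparison.

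Some between-centre difference is plausible from the plan itself. Healing requires absence of tenderness, judged locally, as well as callus. Visit times are approximate. The only bones excluded are those of the hands and feet.

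The as-treated primary analysis raises a second issue. Once children are regrouped by treatment received, balance within centres is no longer guaranteed. If cross-over clusters at sites that heal faster or slower than average, site differences enter the arm comparison as bias, and the direction need not be conservative.

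**Working it through.** **Inputs from the plan.** 300 children, 150 per arm; SD 1 week; margin 1 week; one-sided 0.025; 1:1 blocks of 4 and 6 within centre; 14 sites expecting 2 to 20 patients a year each, 128 in total (Site estimates).

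**Assumption.** The share of healing-time variance lying between centres (ICC) is not in the documents. It is varied from 0 to 0.30.

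**The plan's own figure.** N per group = 2(1.96 + 1.282)² × 1² / 1² = 21.02, which agrees with the stated 21. No centre term enters.

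**Planned precision.** At 150 per arm, half-width = t(0.975, 298 df) × 1 × √(2/150) = 0.227 weeks. With no true difference, the standardised distance to the margin is 1/√(2/150) = 8.66, so power is above 99.99%.

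**Effect of ignoring centre, as randomised.** The centre-adjusted half-width is roughly 0.227 × √(1 − ICC): 0.227 × 0.9487 = 0.215 at ICC 0.10, and 0.227 × 0.8944 = 0.203 at ICC 0.20. A simulation with 14 sites sized in proportion to the site estimates, total SD 1 week and 3,000 trials per setting agrees:

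| Assumed ICC | Half-width unadjusted (weeks) | Half-width with centre (weeks) | Ratio | Coverage unadjusted | One-sided error at margin, unadjusted / with centre |
|---|---|---|---|---|---|
| 0 | 0.2267 | 0.2274 | 0.997 | 95.0% | 0.026 / 0.026 |
| 0.02 | 0.2269 | 0.2255 | 1.006 | 95.3% | 0.027 / 0.027 |
| 0.05 | 0.2264 | 0.2219 | 1.020 | 95.9% | 0.020 / 0.021 |
| 0.10 | 0.2259 | 0.2159 | 1.046 | 96.0% | 0.023 / 0.026 |
| 0.20 | 0.2242 | 0.2036 | 1.101 | 97.0% | 0.017 / 0.023 |
| 0.30 | 0.2234 | 0.1905 | 1.172 | 98.0% | 0.010 / 0.024 |

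The Monte Carlo error of the error rates is about 0.003. At ICC 0.20 the two analyses give different verdicts only if the estimated difference lies between 1 − 0.204 = 0.796 and 1 − 0.224 = 0.776 weeks, taking the two estimates as equal.

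**Effect in the as-treated analysis.** In the pilot (Previous Work), 1 of 7 children randomised to the operating room received emergency department treatment only. As a deliberately adverse assumption, take that rate overall (150/7, about 21 children) and confine it to the seven faster-healing sites. The emergency department group then over-represents fast sites. The unadjusted difference is biased in its favour by about 0.05, 0.07 and 0.09 weeks at ICC 0.05, 0.10 and 0.20. One-sided error at the margin rises from 0.025 to about 0.06, 0.08 and 0.11. With centre in the model the bias disappears and the error returns to 0.02–0.03. If cross-over is unrelated to how fast a site heals, the average bias is nil.

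**Infection.** Expected events at 1% are 300 × 0.01 = 3, spread over 14 or more sites. The stated 91% power at 150 per arm is reproduced by an unstratified normal-approximation interval (0.9105 by exact enumeration, against 0.9111 in the plan's table).

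**The case against.** The strongest reply is that this hardly matters. The plan has 150 per arm for an outcome that needs 21, and the largest change in half-width examined is about 0.03 weeks against a 1-week margin. As randomised, the error is conservative and cannot produce a false claim of non-inferiority. The documents do not show that centres differ: there is one approximate visit schedule, and a single blinded surgeon at the lead site re-reads all radiographs. The plan also expects almost no cross-over in the first 24 hours. The single pilot cross-over came from one centre, so it says nothing about clustering by site. Finally, the simulation treats healing as continuous, whereas it will be observed at visits around weeks 4, 6 and 12.

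Most of this stands, and it is why the point is minor. Two parts do not fully answer it. The central reader covers radiographs only, so tenderness and exact visit timing remain local. The claim that the error is conservative holds for the randomised groups, but the primary analysis is as treated.

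A reader might infer that the healing-time interval is certain to be too wide. The documents do not support that: at ICC 0 to 0.02 the widening is nil or under 1%, and no ICC is given. A reader might also infer that the infection comparison should be stratified by centre. With about 3 expected events there is little to gain, the estimate would be unstable, and the stated power belongs to the unstratified interval.

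**Conclusion.** The mismatch is real and its consequence is small. Centre is the only stratification factor, and the healing-time analysis does not use it. As randomised, the unadjusted interval is wider by about 0%, 2%, 5% and 10% at assumed ICCs of 0, 0.05, 0.10 and 0.20. In the as-treated analysis it can be biased by up to about 0.09 weeks under the adverse cross-over pattern examined (ICC up to 0.20).

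It would be going too far to infer that the Aim 2 conclusion is in danger. A bias of that size plus a half-width of about 0.23 weeks leaves most of the 1-week margin unused unless the true difference is itself close to a week. The raised error rates apply only at that point. These statements rest on the plan's SD of 1 week and on ICCs and cross-over patterns that the documents do not supply. Severity: minor.

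**What to change.** In the Data Analysis section, estimate the healing-time difference and its two-sided 95% interval from a linear model with arm and centre. Pool centres below a pre-stated size by a rule fixed before the data are seen. Use the model for both the as-treated and the intent-to-treat analyses, against the same 1-week margin, and keep the unadjusted interval as a sensitivity analysis.

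Leave the primary infection interval unstratified, and say in one sentence that too few events are expected to stratify by centre.

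The change is to wording only. It uses 13 degrees of freedom with the 14 listed sites, and up to 19 if the 4 to 6 further sites join (20 − 1), out of 300 children. If centres do not differ at all, the adjusted interval is about 0.3% wider (0.2274 against 0.2267 weeks). The model removes differences between centres only; it does not correct for which children cross over within a centre.

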The family will be instructed to look for signs of infection including increased pain, fevers, or odor coming from the cast. All patients will follow up 5-7 days after the injury where the cast will be windowed and the wound examined. This follow-up appointment is standard of care for all Type I open fractures. Infection will be defined as the Surgical Site Infection by the CDC (see Supplementary information section) guidelines. Signs of infection such as erythema and wound drainage will be treated at the discretion of the attending orthopaedic surgeon with additional antibiotics, local wound care, or formal operative debridement. If no signs of infection are noted then the cast will be repaired. Radiographs will be obtained, as is the standard of care, at all follow up visits. Future follow up visits will not include a routine wound examination unless clinically indicated – fevers, increasing pain, foul odor from cast, etc.

Follow up appointments will be standard of care (non-research related) and will be at approximately 1, 2, 4, 6, 12 and 24 weeks post op.

Informed Consent Process:

If the patient agrees to participate he/she will be formally consented and randomized by calling the study coordinator. The study coordinator, or a representative, will be available 24 hours/day to provide the Parent Permission (consent) form, Adolescent Assent form, and HIPAA Authorization form (if separate from the consent form). At each institution, each participant will be consented using the IRB approved consent and assent forms and HIPAA Authorizations of their institution. The study coordinator, or representative, will have digital copies of each participating institutions' consent forms, assent forms, and HIPAA Authorizations in order to obtain consent remotely at that institution. The study coordinator, or representative, obtaining consent will be listed on the authorized personnel list of the institution that joins the study and has IRB approval to obtain consent with this electronic, remote procedure.

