(Specific Aim 2) Union of the fracture will be determined by radiographic parameters of callous being on three of four sides of bone without tenderness to palpation. The radiographs will be read by the attending orthopaedic surgeon at each clinic visit to determine treatment. Loss of reduction will be noted but will not be considered a complication since it can occur whether or not operative debridement was performed. A revision reduction can be performed at the attending orthopaedic surgeon's discretion. In the final analysis phase, an orthopaedic surgeon, blinded to the treatment, at Lurie Children's will be utilized to review all of the patient's radiographs to determine bridging callous on three sides of the bone. This reviewer will be blinded to the patient's name, treatment group but will have access to the length of time since the fracture occurred. Additional procedures or deviations from the protocol will be noted. We will

also carefully examine the rates of anesthesia and sedation related complications including nausea and vomiting, respiratory depression, aspiration, hoarseness, and emergence agitation.

Sample size assumptions and estimates:

This will be a non-inferiority trial as we attempt to demonstrate that ED management is not inferior to OR management.

For the binary outcome of infection (**Specific Aim 1**), we estimate an infection rate of 1% in the reference (OR) group since the literature notes an infection rate between 0% and 5%. Based on a survey of pediatric orthopedic surgeons, an acceptable margin of non-inferiority can be estimated at approximately 4% (i.e., accept a 5% infection rate in the ED group), as the survey suggests surgeons will accept a 5% infection rate in order to avoid formal operative treatment of children with open fractures. We will test the following hypotheses: $H_0: P_T - P_C \geq \Delta$ vs. $H_1: P_T - P_C < \Delta$. In order to test these hypotheses in a non-inferiority design at the one-sided 2.5% level of significance, we will construct a two-sided 95% confidence interval for the difference in proportion of infections ($P_T - P_C$) across the two groups. If the upper confidence limit is less than our acceptable margin of non-inferiority ($\Delta=4\%$), then we would conclude ED management is not inferior to OR management with respect to infection rates.

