Our results suggest that a **sample size of 150 per group (300 total)** would provide 91% power to detect non-inferiority of emergency room management when compared to operating room treatment in the type one open fractures under the assumptions outlined above. We have accepted a 5% infection rate (4% shift from the hypothesized reference rate). If the baseline infection rate is 2%, this study would be adequately powered (87%) to show non-inferiority for a margin of 5% (7% infection rate in the ED arm). As the calculation above illustrates, the study is also well powered to demonstrate non-inferiority with respect to healing time.

Site estimates:

The following sites have provided the initial estimates as to how many patients they feel could be enrolled in a given year: Lurie Children’s = 2/year, Vancouver Children’s Hospital 5/y, Riley Children’s= 2/y, University of Mississippi Medical Center = 9/y, Mary Bridge Children’s Hospital= 12/y, Yale-New Haven Children’s Hospital= 4/y, Carrie Tingley Children’s Hospital= 20/y, Phoenix Children’s Hospital= 20/y, Nationwide Children’s Hospital= 20y, IWK Health Centre, Halifax=4/y, Denver Children’s Hospital=12/y. Texas Children’s Hospital= 12/y, Morristown Medical Center = 2/y, New York University Medical Center = 4/y. Approximate Total= 128/y.

Subject Recruitment:

The number of subjects needed for this trial is large. To date, the pilot study has had an excellent recruitment (80% see below) rate, so we expect similar rates at participating centers.

Currently, with the 14 sites who have agreed to participate thus far, the expected recruitment is 128 patients per year. We plan to add 4-6 more sites during the Planning Grant Period which would expand the projected total recruitment to 160 patients per year. Therefore, when the study is at full capacity, we conservatively anticipate recruiting 120 patients per year (assuming 75% recruitment rate) over the 3 year grant period, for a total of 360 patients, which surpasses the calculated 300 patients needed for adequate statistical power. We are accepting and powering for a 5% infection rate in the ED arm. If we were to accept a 6% infection rate (i.e., a 5% margin of non-inferiority) then we would require only 190 patients. For a 7% infection rate ($\Delta=0.06$), we will need 150 patients. If recruitment is lower than expected, we could accept a larger

margin of non-inferiority given the large range of type I open fracture rate (0-10%) in the literature.

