If we are only able to recruit 150 patients, and the rates of infection in the OR and ED groups are nearly equal, we will consider halting the study and releasing the results. This will be decided by the Steering Committee in conjunction with the funding agency. Alternatively, the Steering Committee could decide to prolong the study to achieve increased numbers for the comparison.

Data management:

An initial hard copy survey of the initial data will be completed by the attending surgeon with the study coordinator's assistance. Data collected will include name, MRN, telephone number, age, injury mechanism, bone fractured, wound size (in cm), wound location, state of skin, neurovascular status, comorbid conditions, antibiotics given, tetanus status, surgical procedure description and anesthesia/sedation complications. At the 1-week follow up visit, a survey will be completed by the attending surgeon which will ask if fevers are/have been present, wound drainage through cast, skin and wound examination (erythema, drainage), whether additional antibiotics are necessary, and the reduction of the bone on radiographs. The survey completed by the treating orthopaedic surgeon at subsequent visits will also ask if fevers are presents, if pain has increased, wound drainage, if a second look at the wound was necessary, reduction of the fracture, and healing.

An online database has been created using REDCap technology. Name, MRN and telephone number will be recorded in site-specific Excel files. Non-identifying data will be recorded in REDCap. Information from the initial and follow up visits will be entered into the databases by the surgeon or his representative which will be password protected. Each patient will have a unique identifier. Randomization allocation can also be found through the REDCap site.

Data Analysis:

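### Aim 2 is sized and tested as if healing time were observed exactly, but union is seen only at visits, with a six-week gap after week 6

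*Combined protocol and SAP*

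**What the plan says.** - **When healing can be seen.** Under Follow up visit description and schedule, appointments "will be at approximately 1, 2, 4, 6, 12 and 24 weeks post op", with radiographs at each.
- **What counts as union.** Ascertainment of response variables (Specific Aim 2) requires callus on three of the bone's four aspects and a non-tender fracture site, so a film and an examination are both needed. "The radiographs will be read by the attending orthopaedic surgeon at each clinic visit to determine treatment". A blinded surgeon later rereads the films for callus and "will have access to the length of time since the fracture occurred". Under Data management, the form for later visits asks "if a second look at the wound was necessary, reduction of the fracture, and healing".
- **How Aim 2 is sized.** Sample size assumptions and estimates states that "most fractures have a healing time of 6 weeks with an estimated standard deviation of 1 week". With a 1-week margin, one-sided 0.025 and 90% power, it obtains 21 per arm. After setting 150 per arm on infection, it adds that "the study is also well powered to demonstrate non-inferiority with respect to healing time".
- **How Aim 2 is decided.** Data Analysis says "an independent two-sample confidence for difference in mean healing time will be constructed and used in the same manner" as for infection. The plan will also "use Kaplan-Meier estimation to create curves comparing cumulative incidence of infection as well as time to healing".

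No section says which date is recorded as the healing date, whether the attending's or the blinded reader's assessment defines union, or that an interval-censored method will be used.

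**The concern.** The planned mean of 6 weeks falls on a visit that is followed by six weeks without one. If healing times are roughly symmetric about 6 weeks, about half the children unite in that gap and are first seen united at about week 12. The recorded variable then takes very few values, its spread is far wider than 1 week, and a difference in recorded means is not a difference in true weeks. The 1-week margin is nevertheless applied to it directly.

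Two things are at stake. The 21 per arm, and the claim of ample power built on it, describe a variable the trial will not observe. And the Aim 2 result can turn on a dating rule that is not fixed before the data are seen, in an unblinded trial.

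**Working it through.** **Inputs from the plan:** visits at weeks 1, 2, 4, 6, 12 and 24; healing mean 6 and SD 1; margin 1 week; one-sided 0.025; 150 per arm, 1:1.

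**Assumptions:** Normal healing times; no dropout; differences taken as ED minus operating room (OR). Because the plan gives no dating rule, two are tried: the first visit showing union, and the midpoint between that visit and the one before.

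**1. The plan's own figure.** N = 2(1.96 + 1.282)² × 1² / 1² = 21.02. The 21 per arm reproduces, but only if each healing time is known exactly.

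**2. What is recorded at mean 6, SD 1.** P(union in weeks 2–4) = 0.023, in weeks 4–6 = 0.477, in weeks 6–12 = 0.500.
- First visit (values 4, 6, 12): mean 8.95, SD 3.06.
- Midpoint (values 3, 5, 9): mean 6.95, SD 2.07.

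**3. Sample size for 90% power with equal healing.** N = 2(1.96 + 1.282)² × SD².
- First visit: 21.02 × 3.06² = 197 per arm.
- Midpoint: 21.02 × 2.07² = about 90 per arm (91 if the rounded SD is used and N rounded up).

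**4. Power with equal healing.** SE = SD × √(2/n); power = Φ(1/SE − 1.96).
- At 150 per arm, first visit: SE 0.353, power 0.81.
- At 150 per arm, midpoint: SE 0.239, power 0.99.
- At 21 per arm: 0.18 and 0.35, against the planned 0.90.

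**5. Chance of declaring non-inferiority at 150 per arm, visits on schedule.** P = Φ((1 − recorded difference)/SE − 1.96), with SE from both arms' recorded SDs.

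| True means, OR v ED | First visit: recorded difference, pass | Midpoint: recorded difference, pass | Exact dating: pass |
|---|---|---|---|
| 6 v 6 | 0, 81% | 0, 99% | >99.9% |
| 6 v 6.5 | 1.18, 0.6% | 0.80, 14% | 99% |
| 6 v 7 | 2.09, about 0% | 1.41, about 0% | 2.5% |
| 7 v 8 (assumed) | 0.82, 15% | 0.55, 94% | 2.5% |

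Starting from a mean of 6, a true delay of only 0.42 weeks (first visit) or 0.65 weeks (midpoint) is already recorded as a full week.

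**6. Sensitivity (simulation, 4,000 trials per setting).**
- Visit dates varying with SD 10% to 15% of nominal time: equal-healing power is 76–81% (first visit) and 99% (midpoint). A half-week delay passes 2–4% and 24–30%.
- Healing SD of 0.75 or 1.5: equal-healing power is 82% or 76% (first visit) and 99% or 97% (midpoint).
- Assumed 7 v 8 weeks, as date variation goes from 15% to none: a true 1-week delay passes 1–17% (first visit) and 15–91% (midpoint; the formula in step 5 gives 94% with no variation).

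**The case against.** - **Equal healing, the case the plan sized for, keeps reasonable power.** The plan's formula has no true-difference term, and at 150 per arm power is 81% or 99%. The 18% and 35% figures describe a trial of 21 per arm that nobody intends to run. This stands: the power claim is weakened, not overturned. What does not survive is the 21 itself, or the ability to pass a small acceptable delay.
- **Healing may centre earlier.** The plan's remark about 6 weeks could mean that most children are judged healed at the week-6 visit. At an assumed mean of 5 weeks, power with equal healing is 94% or 99.9%. A half-week delay still passes only about 1% or 17% of the time.
- **Visits are only approximate, Kaplan-Meier curves are planned, and exact methods will be explored.** Date variation at the levels tried does not rescue the half-week case. Standard Kaplan-Meier handles right censoring, not events known only to lie between visits, and it carries no non-inferiority rule. Exact methods change how the interval is computed, not what is recorded.
- **A blinded reader has time since fracture.** That dates each film; it does not date union between films.

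A reader might also infer that the plan is likely to pass an inferior treatment on healing. The plan's own inputs do not support this: at mean 6 and SD 1 a true 1-week delay passes about 0% of the time. The high pass rates need a later mean that the documents do not give, and the highest also need midpoint dating and visits exactly on schedule. Nor does counting visits from surgery create a material offset between arms: surgery is within 24 hours, and the first visit is timed from injury.

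**Conclusion.** The 21 per arm and the plain comparison of means are wrong as written for the variable this trial will record. On the plan's mean and SD, with Normal healing times and either dating rule, the recorded SD is two to three times the planned value and the sample size for 90% power is roughly four to nine times 21. A half-week delay that exact dating would pass 99% of the time passes at most 14% with visits on schedule, or 30% with dates varying by 15%.

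The consequence is mainly lost efficiency on the second clinical aim. At the planned mean the error is conservative. False non-inferiority arises only if healing is later than planned, at an assumed control mean of about 7 weeks or more, and its size depends on the dating rule and on visit-date variation. It would be wrong to conclude that the trial is too small: infection sets the total of 300, and neither that total nor Aim 1 is affected.

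**What to change.** **Data Analysis and Ascertainment of response variables.**
- Record actual visit dates, counted from injury in both arms.
- State whose reading defines union, and how the blinded callus reading is combined with the clinic finding on tenderness.
- Make the Aim 2 comparison with an interval-censored model, from the last visit without union to the first with it, using a likelihood-based 95% interval for the mean difference.
- Replace the Kaplan-Meier healing curve with an interval-censored curve.
- Prespecify sensitivity analyses: an alternative healing distribution, and the difference in proportions united by weeks 6 and 12.

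**Sample size assumptions and estimates.** Restate the Aim 2 sample size and power for the recorded variable. Under the interval-censored Normal model the simulated SE at 150 per arm was 0.138, so 90% power needs 150 × (3.242 × 0.138)² = about 30 per arm.

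**What it buys.** In simulation at 150 per arm and mean 6, a Normal interval-censored model with a likelihood-based limit passes a half-week delay in 87–90% of trials and a 1-week delay in 2.5–3.2%.

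**Cost.** Wording only; no added visits, films or patients. The estimate does depend on the assumed distribution.
- With dates varying by 10%, a gamma shape gave nearly the same results as the Normal. A strongly skewed shape overstated a 1-week delay (1.17 weeks, the conservative direction).
- With visits exactly on schedule the model rests on the few children who unite early. A rough lognormal check then passed a true 1-week delay about 26% of the time, and at an assumed control mean of 7 weeks the Normal model is inconclusive.

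The model-based difference should therefore always be reported with the sensitivity analyses.
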